7.9.3 Vital signs

Vital signs, including measurements of respiratory rate (breathes per minute), heart rate (beats per minute), and BP (mmHg), will be listed and summarized for actual values and change from baseline with descriptive statistics for the As-Treated and PSC populations by Timepoint (Baseline Monitoring, Day of Implant, Congestion Target Met, Post 72Hrs or Discharge and Follow-Up).

Vital signs measurements collected from the time of implant until Post 72Hrs or Discharge will be presented graphically for each patient and each parameter for As-Treated and PSC populations.

7.9.4 Cardiovascular Examination

Cardiovascular examination measurements will be listed and summarized by Timepoint (Pre-Implant, Day of Implant, Congestion Target Met, Day of Retrieval, Post 72Hrs or Discharge and Follow-Up) with descriptive statistics for the As-Treated population by subgroup and overall.

7.9.5 Hemodynamic parameters

Hemodynamic parameters, including measurements of CVP, PCWP, SaO₂, SvO₂ and PA Pressure (Systolic, Diastolic and Mean) will be listed for As-Treated and PSC populations.

Summary of CVP, PCWP and PA Pressure (Systolic, Diastolic and Mean) at Baseline and Once Congestion Target is Met will be provided along with the summary of change from Baseline to Once Congestion Target for As-Treated and PSC populations.

Measurements of CVP, PCWP and PA Pressure (Systolic, Diastolic and Mean) collected starting from the time of implant will be presented graphically for each patient and each parameter for As-Treated and PSC populations.

Boxplots of CVP and PCWP will be provided by subgroup and overall to compare baseline results with Congestion Target Met and Retrieval (defined as the last non-missing measurement collected during Aortix Therapy) for As-Treated population.

7.9.5.1 Cardiac Output and Cardiac Power Output

Cardiac Output (CO) and Cardiac Power Output (CPO) are derived parameters that will be associated with hemodynamic measurements of SaO₂ and SvO₂ (including date and time). Calculations will be based on the last non-missing measurements of Height, Weight, Blood Hemoglobin (BH), Systolic and Diastolic Blood Pressure at Baseline and Once Congestion Target is Met.

Cardiac Output (mL/min) is calculated as:

$$\text{Cardiac Output} = \frac{\text{O}_2 \text{ consumption}}{\text{Arteriovenous O}_2 \text{ difference}} = \frac{125 \left[\frac{\text{ml O}_2}{\text{min m}^2} \right] * \text{BSA}}{13 * \text{BH} * (\text{S}_a\text{O}_2 - \text{S}_v\text{O}_2)},$$

where Body Surface Area (BSA) is calculated through Haycock's formula:

$$\text{BSA} = 0.024265 * (\text{Height [cm]})^{0.3964} * (\text{Weight [kg]})^{0.5378}.$$

Cardiac Power Output (W) is calculated as:

$$\text{Cardiac Power Output} = \frac{\text{Mean Arterial Pressure} * \text{Cardiac Output}}{451},$$

where Mean Arterial Pressure is calculated by:

$$\text{Mean Arterial Pressure} = \frac{\text{Systolic Blood Pressure} + 2 * \text{Diastolic Blood Pressure}}{3}.$$

Summary of CO and CPO at Baseline and Once Congestion Target is Met will be provided along with summary of change from Baseline to Once Congestion Target for As-Treated and PSC populations.

Detailed listing of CO and CPO will be provided along with all associated measurements for As-Treated and PSC populations .

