The Aortix System has undergone extensive pre-clinical verification and validation studies to confirm device performance and safety requirements following internationally recognized standards and guidance. The Aortix System has also been tested *in vivo* using large-animal (porcine and ovine) models, successfully demonstrating deployment, retrieval, and acute efficacy. Initial safety and efficacy data were obtained in a porcine model and demonstrated proof of concept (n=9).²⁵ In an ovine model of chronic HF (n=4), the Aortix Pump decreased the energy consumption of the heart by 39%, shifting it to a more efficient operating point. Cardiac output (+14%) and ejection fraction (+28% [relative]) were significantly increased, as were key measures of renal function, eGFR (+23%) and urine output (+100%). These *in vivo* data supported the use of the Aortix System in a first-in-human (n=6) study for acute use during high risk percutaneous coronary intervention (HR-PCI) which demonstrated procedural and device feasibility and safety followed for 14 days.

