4.5 Aortix Post-Deployment Monitoring and Management

The Aortix Pump has been tested to operate safely for 7 days of use. Aortix therapy should continue until objective signs of hemodynamic congestion have resolved, alternative / escalated therapy is required, or if device related safety concerns arise. The duration of Aortix pump use should be dictated by the physician's target for diuresis (net fluid and weight loss). In addition, the pre-specified target for pump effectiveness is a **minimum 20%** decrease in the patient's CVP and PCWP from pre-implant. **Diuretics and inotropes should not be adjusted for twelve (12) hours after the Aortix pump is turned on. After that point, while the Aortix pump is running, cessation of medications or down titration of diuretics, inotropes or other heart failure medications are allowed.** Adjustments of other medical therapy can otherwise be made at any point during the study period at the discretion of the treating physician. All medications and medications adjustments will be captured on eCRFs.

Refer to the Aortix System Instructions for Use (PPL004) for details of the Aortix Pump management.

If clinically significant device migration is suspected, use x-ray or another imaging modality to verify pump position.

It is recommended that the patient's vital signs be monitored frequently post procedurally (e.g., vitals checked every 15 minutes for the first hour, then every 30 minutes for the second hour). The patient's pedal pulses should be monitored post procedurally frequently for distal limb perfusion, ideally but not limited to, every fifteen (15) minutes times four (4), every thirty (30) minutes times two (2) and every hour (1) for two (2) hours and then as frequently as signs and symptoms warrant. In addition, the access site should be monitored for bleeding, hematoma, swelling or signs of infection.

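### Updating weight in the assumed-oxygen-consumption formula lets fluid loss by itself lower computed cardiac output and cardiac power output

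*SAP*

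**What the plan says.** SAP 7.9.5.1 derives CO as assumed oxygen consumption divided by the arteriovenous oxygen difference. The numerator is 125 mL O2/min/m² times BSA. BSA comes from the Haycock formula, in which weight has the exponent 0.5378. The denominator is 13 times blood hemoglobin times (SaO2 - SvO2). CPO is mean arterial pressure times CO, divided by 451.

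On which inputs to use, the SAP says: "Calculations will be based on the last non-missing measurements of Height, Weight, Blood Hemoglobin (BH), Systolic and Diastolic Blood Pressure at Baseline". The sentence goes on to name the second timepoint: "Systolic and Diastolic Blood Pressure at Baseline and Once Congestion Target is Met". The planned output includes a "summary of change from Baseline to Once Congestion Target for As-Treated and PSC populations".

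Protocol 4.5 says the duration of pump use should follow the physician's "target for diuresis (net fluid and weight loss"). Weight is part of the cardiovascular exam on the day of implant (Protocol 4.4.1) and at the congestion-target assessment (Protocol 4.5.3). Appendix A also schedules that exam at baseline monitoring. Height is collected once.

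Neither document holds weight fixed across the two CO calculations, specifies a dry weight, or mentions the effect of weight change on computed CO.

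**The concern.** Oxygen consumption is assumed in proportion to BSA, so a change in weight between the two timepoints changes the numerator of CO without any change in a measured circulatory quantity. Two patients with the same change in saturations, hemoglobin and blood pressure would be recorded with different changes in CO and CPO if one lost more fluid. Fluid loss is what the therapy aims at, so weight will tend to move in one direction where therapy works, and the shift is largest in those who lose most.

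Change in CO and CPO is listed in Protocol 3.3.4 and SAP 5.4 among the additional data to be reported. The study is also meant to inform the design of later studies (Protocol section 7, SAP 2.3), so a diluted estimate of the CO change could be carried forward.

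**Working it through.** The documents give no numerical CO, CPO or expected change for these patients, and the sample size was not statistically derived, so there is no figure in the plan to reproduce. The check is algebra on the SAP's own formulas.

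**Formulas (SAP 7.9.5.1)**

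- BSA = 0.024265 × Height^0.3964 × Weight^0.5378
- CO = 125 × BSA / [13 × BH × (SaO2 - SvO2)]
- CPO = MAP × CO / 451

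**Isolating weight.** Hold height, hemoglobin, saturations and MAP fixed and let weight go from W1 to W2. All other terms cancel:

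CO2/CO1 = CPO2/CPO1 = (W2/W1)^0.5378

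For small changes this is about 0.54% of CO per 1% of weight. Height drops out.

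**Size.** The weights below are assumptions.

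| Starting weight | Loss | (W2/W1)^0.5378 | Change in CO and CPO |
|---|---|---|---|
| 90 kg | 2 kg | (88/90)^0.5378 = 0.988 | -1.2% |
| 90 kg | 5 kg | (85/90)^0.5378 = 0.970 | -3.0% |
| 90 kg | 10 kg | (80/90)^0.5378 = 0.939 | -6.1% |
| 110 kg | 5 kg | (105/110)^0.5378 = 0.975 | -2.5% |
| 110 kg | 10 kg | (100/110)^0.5378 = 0.950 | -5.0% |

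**In absolute units.** Take an assumed patient: 170 cm, 90 kg, BH 12 g/dL, SaO2 0.96, SvO2 0.56, BP 110/70.

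- BSA = 2.09 m² and assumed oxygen consumption = 125 × 2.09 = 261 mL/min
- CO = 261 / (13 × 12 × 0.40) = 4.19 L/min
- MAP = (110 + 2 × 70)/3 = 83.3 mmHg, so CPO = 83.3 × 4.19 / 451 = 0.774 W
- A 5% weight loss alone lowers CO by 0.11 L/min and CPO by 0.021 W. A 10% loss lowers them by 0.23 L/min and 0.043 W.

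The SAP labels CO as mL/min. With these input units the formula gives L/min, which dividing by 451 also needs. The percentages do not depend on this, but the label should be corrected.

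**Against a CO change of a known size.** The only CO effect in the documents is from the ovine model in Protocol 1.1 (n=4): "Cardiac output (+14%) and ejection fraction (+28% [relative]) were significantly increased". It is used here for scale only. If the change from the other inputs is +14%, the reported change is 1.14 × (W2/W1)^0.5378 - 1, and the share hidden is (14 - reported)/14.

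| Starting weight | Loss | Reported change | Share of +14% hidden |
|---|---|---|---|
| 90 kg | 2 kg | 1.14 × 0.988 - 1 = +12.6% | about 10% |
| 90 kg | 5 kg | 1.14 × 0.970 - 1 = +10.5% | about 25% |
| 90 kg | 10 kg | 1.14 × 0.939 - 1 = +7.0% | about 50% |
| 110 kg | 5 kg | 1.14 × 0.975 - 1 = +11.2% | about 20% |
| 110 kg | 10 kg | 1.14 × 0.950 - 1 = +8.3% | about 41% |

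**With one BSA per patient.** The weight ratio becomes 1, and a +14% change is reported as +14.0% whatever the weight loss.

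**The case against.** - **Standing of the outcome.** CO and CPO are in neither the study objectives nor the primary effectiveness endpoints. They are summarized descriptively. The only planned test, the Wilcoxon signed-rank in SAP 7.8.3, covers CVP, PCWP, BNP and NT-pro-BNP. This stands and limits the importance of the point.
- **Another CO measure is planned.** Echo CO is recorded at baseline, echo is repeated at the congestion-target assessment, and changes in echo parameters are reported. The SAP also lists CO and CPO with all their inputs, so a reader could recompute them with a fixed weight. This stands too, but the summary table would still carry the weight component.
- **Net error is unknown.** Oxygen consumption is never measured, and the documents do not say how it changes during therapy. Other errors can be of similar size: with an assumed 40-point saturation difference, a 1-point error in SvO2 moves computed CO by about 2.5% (1/40). A reader might infer that the reported change in CO is too low overall. The documents do not support that, because they show the direction of the weight component and not of the total error.
- **The weights are assumed.** Losses may be small, particularly as the later timepoint includes patients whose therapy was deemed ineffective. A patient who gains weight is shifted upward. SAP 7.14 says, in connection with urine output, that the congestion-target timepoint is not in the latest CRF. If an earlier weight were carried forward, the effect would shrink and would vary between patients.
- **Direction.** Where weight falls, the component works against the device, so it would not inflate a claimed benefit. That is true, but a diluted estimate is still a poor input to later design.

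A reader might also infer that the plan builds a false negative association between fluid loss and CO into its results. Neither document plans an analysis relating the two, so no specified output is affected in that way.

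**Conclusion.** The point holds as a limited analysis-choice issue. As SAP 7.9.5.1 is written, weight loss between Baseline and the congestion-target timepoint by itself multiplies computed CO and CPO by (W2/W1)^0.5378. The algebra is exact and needs only that a separate weight is used at each timepoint, which the SAP specifies. The sizes rest on assumed weights and, for the share hidden, on borrowing a four-animal effect as a yardstick. On those terms the component is modest in itself but not negligible beside a CO change of that order.

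It should not be read as a fault in a primary endpoint or in a formal test of the device's mechanism, since CO and CPO are additional descriptive data. The change is worth making because it removes a component tied to the intended treatment effect and needs no new data.

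**What to change.** In SAP 7.9.5.1, state that BSA is computed once per patient from height and a single pre-implant weight, and that this BSA is used at both timepoints for the change in CO and CPO. Only SaO2, SvO2, hemoglobin and blood pressure then vary.

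Name the Day of Implant weight, and state it as an exception to the baseline rule in SAP section 4. That rule would otherwise select the last Baseline Monitoring weight, whereas Appendix A first schedules SaO2 and SvO2 on the day of implant. Keep the version with current weight at each timepoint as a sensitivity summary.

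The cost is a short addition to the SAP, a small programming change and one extra summary, with no new data or visits. The downside is that absolute CO and CPO, and their absolute change, remain scaled to the congested pre-implant weight. Only the percentage change is freed of the weight component, so it should be reported alongside the absolute change.

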After signing informed consent, a urinary collection device will be placed, if not already present. A Foley catheter is recommended, but an external urine collection device may be used per institution requirements. The urine collection device will be placed (do not measure the urine collected during catheter placement) at least twelve (12 hours) before the Aortix Pump placement. If a urinary collection device is already in place, urine should be discarded. Output and intake should be strictly observed starting twelve hours prior to the scheduled implant. The urine collection device and the strict ins/outs monitoring will continue until the Aortix pump is retrieved. The first measurement of intake and output should occur at least six hours prior to Aortix placement and should be recorded every two hours until the pump is turned on. Measurements will occur at the frequency outlined in **Appendix A**.

Fluid ins should be monitored (IV and Oral) for the entire duration the urine collection device is in place with final measurements taken at the time of device retrieval.

Patients will receive standard medical therapy throughout the study. Patients should be on optimized medical therapy prior to being considered for Aortix Pump placement. To characterize the effect of the experimental device, physicians should not adjust the diuretic or inotrope dosing regimen during the twelve (12) hours prior to or the twelve (12) hours after Aortix Pump placement, unless medically necessary. **Diuretics and inotropes should not be adjusted for twelve (12) hours after the Aortix pump is turned on, however, after that point, while the Aortix pump is running, cessation of medications or down titration of diuretics, inotropes or other medications are allowed.** Adjustments of medical therapy can otherwise be made at any point during the study period at the discretion of the treating physician. All medications and medications adjustments will be captured on eCRFs.

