	Pre-Implant Period (Baseline Monitoring)	Day of Implant (Pre-implant)	Implant to Pump Retrieval					Once Congestion Target is Met and within 12 Hours of Beginning Weaning ^α	Day of Pump Retrieval (Pre-Pump Retrieval)	Cath-Lab Pre-Pump Retrieval	Post-Pump Retrieval Monitoring		Follow-Up: 30 days (± 7 days) from Pump retrieval
	Current hospitalization once	once	Once (after pump deployed)	2 hours post implant (± 30 min)	6 hours post implant (± 30 min) and Every 6 hours (± 1 hour) for 24 hours post implant	Every 24 h (± 2 hours) ◆	Pump Speed Changes #	once	once	once	Every 24 h (± 2 hours)	Once at 72 hours post retrieval (± 4 hours) or discharge (whichever is earlier)	once
HEMODYNAMICS													
CVP#		X		X	X	X	X	X		X			
PA Pressure Systolic#		X		X	X	X	X	X		X			
PA Pressure Diastolic#		X		X	X	X	X	X		X			
PA Pressure Mean#		X		X	X	X	X	X		X			
PCWP #		X		X		X	X	X		X			
CO, CPO**		X		X	X	X		X		X			
• SvO2		X		X	X	X		X		X			
• SaO2 via pulse oximeter		X		X	X	X		X		X			

PCWP, CVP and PA Pressures – these values should also be collected any time the speed of the pump is adjusted. For PCWP it should be within 2 hours (+/- 30 min) of a speed change. For CVP and PA Pressures it should be within 1 hour (+/- 30 min) of a speed change.

** Cardiac Output (CO) and Cardiac Power Output (CPO) will be calculated by the sponsor. CPO parameters to be collected on the hemodynamics case report form: SaO2 (as measured by pulse oximeter), SvO2 (as measured on mixed venous gas from PA catheter).

◆ First measurement should be made 24 hours after pump is turned on. Subsequent every 24 hour measurements can be made during daily rounds or another convenient time as long as the first every 24 hour measurement is made at least 12 hours after the initial measurement 24 hours after the pump is turned on.

α One time assessments to be taken once congestion targets are met or therapy has been deemed ineffective (decision has been made to retrieve device). These assessments should be performed before the pump speed is turned down; within 12 hours of beginning weaning.

Blood and Urine Labs

Category	Pre-Therapy		Aortix Therapy				Post-Therapy			
	Pre-Implant Period (Baseline Monitoring)	Day of Implant (Pre-implant)	Implant to Pump Retrieval			Once Congestion Target is Met and Within 12 hours of Beginning Weaning ^a	Cath-Lab Pre-Pump Retrieval	Post-Pump Retrieval Monitoring		Follow-Up: 30 days (± 7 days) from Pump retrieval

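### SAP 7.9.5.1 compares cardiac output and power only at Baseline and congestion target met: the readings taken while drug doses are held are not compared, and baseline inputs can come from different days

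*SAP*

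**What the plan says.** Change in CO and CPO is a listed outcome (Protocol 3.3.4, SAP 5.4). No timepoints are attached to it there.

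The Hemodynamics table in Protocol Appendix A has a CO/CPO row. It is marked at pre-implant, 2 h, 6-hourly to 24 h, every 24 h, congestion target met, and in the cath lab before retrieval. A footnote gives the "CPO parameters to be collected on the hemodynamics case report form": SaO2 and SvO2.

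SAP 7.9.5.1 says that CO and CPO "are derived parameters that will be associated with hemodynamic measurements of" SaO2 and SvO2, with date and time. It then takes the last non-missing height, weight, hemoglobin, and "Systolic and Diastolic Blood Pressure at Baseline and Once Congestion Target is Met". The planned table is equally narrow: "Summary of CO and CPO at Baseline and Once Congestion Target is Met will be provided along with summary of change". A listing is also promised, without named timepoints.

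Protocol 4.3 gives the reason for holding drug doses around implant: "To characterize the effect of the experimental device, physicians should not adjust the diuretic or inotrope dosing regimen during the twelve (12) hours" before and after placement, unless medically necessary. After 12 h on the pump, "cessation of medications or down titration of diuretics, inotropes or other heart failure medications are allowed" (Protocol 4.5).

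SAP Section 4 sets the default baseline as the last value from Baseline Monitoring. It moves to the last value before implant only for parameters not collected at that visit.

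**The concern.** The protocol sets up a period of stable drug dosing so that the device's effect can be described, and it schedules CO/CPO readings inside that period. The SAP's only planned comparison ends at a later reading, when inotropes may already have been reduced or stopped. Inotropes act on cardiac output, so in a patient who was on one, the reported change is the pump effect net of any inotrope reduction.

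The second issue concerns the baseline value itself. CPO multiplies a mean arterial pressure (MAP) by a CO. Under the default baseline rule the two can come from different visits, and this applies whether or not the patient is on inotropes.

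At stake is how the pilot describes the claimed mechanism of higher output (Protocol Section 2, Aortix Pump), in a study meant to inform the design of later ones (Protocol Section 7).

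**Working it through.** **1. Scheduled CO/CPO readings.** The documents give no total, so this is a count of the marks in the Appendix A row, with the 24 h reading counted once. Support runs from 2 days (initial minimum, Protocol 4.5.2.1) to 7 days (tested duration, Protocol 4.5).

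- 2 days: pre-implant 1 + 2 h 1 + 6/12/18/24 h 4 + 48 h 1 + target met 1 + cath lab 1 = 9.
- 7 days: the same, with 6 later daily readings in place of 1 = 14.
- If the target-met reading coincides with a daily one, which Protocol 4.5.3 allows: 8 to 13. If 24 h is counted in both columns: 10 to 15.

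The SAP summarises 2 of these: 2/9 = 22% down to 2/14 = 14%.

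**2. What is scheduled when (Appendix A).**

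| Input | Baseline Monitoring | Day of Implant | 2 h | 6 h | 12 h | Target met |
|---|---|---|---|---|---|---|
| SvO2, SaO2 | no | yes | yes | yes | yes | yes |
| Blood pressure | yes | yes | yes | yes | yes | yes |
| Hemoglobin | no | yes | no | no | yes | yes |
| Weight | yes | yes | no | no | no | yes |

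At 12 h, only weight has to be carried forward. At 2 h and 6 h, hemoglobin must be borrowed as well. The 12 h reading carries a ±1 h window, so it can fall on either side of the end of the no-adjustment period.

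**3. One patient whose inotrope is withdrawn.** Assumptions: a pump effect of +14%, borrowed from the protocol's four-animal ovine result ("Cardiac output (+14%) and ejection fraction (+28% [relative]) were significantly increased"); a fall in CO on withdrawal of 5% to 20%, which the documents do not give; and effects that multiply.

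- 1.14 × 0.95 = 1.083, shown as +8.3%.
- 1.14 × 0.80 = 0.912, shown as -8.8%.
- The sign changes when the fall exceeds 1 - 1/1.14 = 12.3%.

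**4. Group mean.** The number of trial patients on inotropes is not given. Protocol 1.1 cites 6% to 12% use in acute decompensated heart failure. Suppose every such patient had withdrawal:

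- 6% with a 5% fall: 1.14 × (1 - 0.06 × 0.05) = 1.14 × 0.997 = 1.137, or +13.7%.
- 12% with a 20% fall: 1.14 × (1 - 0.12 × 0.20) = 1.14 × 0.976 = 1.113, or +11.3%.
- Even with a 20% fall, the mean would reverse sign only if more than 0.123/0.20, about 61%, of patients had withdrawal.

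**5. Baseline inputs.** By the table in step 2 and SAP Section 4, baseline blood pressure and weight come from Baseline Monitoring, while SvO2, SaO2 and hemoglobin come from the Day of Implant. CPO is proportional to MAP. With illustrative MAPs of 80 mmHg at Baseline Monitoring and 75 mmHg on the Day of Implant, baseline CPO is overstated by 80/75 - 1 = 6.7%. Weight matters less: it enters body surface area to the power 0.5378, so a 5% loss lowers CO by 1 - 0.95^0.5378 = 2.7%.

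**The case against.** The strongest reply is that the early readings are not lost. CO/CPO is tied to dated saturation readings, and a "Detailed listing of CO and CPO will be provided along with all associated measurements for As-Treated and PSC populations". SAP 3.1 puts all study data in listings and presents data at scheduled timepoints where applicable, SAP 7.9.5 lists SaO2 and SvO2, and Protocol Section 7 says each patient will be reviewed individually. This stands to a point. A reader might infer that the readings made while doses are held are never used. The documents do not support that: the pre-implant saturations lie in the same window and serve as baseline, and later readings may appear in listings. What is missing is any summary or comparison of the on-pump ones. If CO/CPO were derived at 12 h for the listing, the SAP would still name blood pressure, hemoglobin and weight only at the two timepoints, so the rule needs repair on either reading.

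Inotrope change is also analysed: doses by timepoint in SAP 7.4 and stage shifts in SAP 7.4.3. That helps identify affected patients, but nothing links it to CO/CPO.

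A reader might also infer that SAP 7.14 conceals a departure from the protocol. It does not. Appendix A is a collection schedule, Protocol 3.3.4 fixes no CO/CPO timepoints, and pre-implant versus target met is the timeframe the protocol uses for its pressure and natriuretic peptide endpoints.

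Finally, Protocol 4.4.1 lets tests done on the day of implant serve both visits, so the baseline mismatch arises only when the visits fall on different days. That limits how often it occurs but does not remove the rule.

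**Conclusion.** The point holds in two limited parts, and both are worth correcting before the tables are programmed.

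First, the SAP summarises CO/CPO at 2 of about 9 to 14 scheduled readings and compares none of the 2, 6 and 12 h readings. For an individual on an inotrope the target-met change can be materially distorted (+8.3% to -8.8% under the stated assumptions). It is tempting to infer that the study's overall CO result would be reversed. The documents do not support that: at the cited 6% to 12% use, the illustrative mean stays between +13.7% and +11.3%. Actual use in this refractory population could be higher, although exclusion criterion 1 removes patients on more than 1 unit in the previous 48 h.

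Nor would the 12 h reading isolate the pump effect. The design is uncontrolled, oxygen consumption is assumed at 125 mL/min/m², the reading follows an invasive procedure, and medically necessary dose changes are permitted. It removes planned drug adjustment as an explanation, and no more.

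Second, the default baseline rule can pair a MAP and a CO from different days. This follows directly from the text; its size depends on how far blood pressure moves between the visits, and the 6.7% is only an example.

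**What to change.** Amend SAP 7.9.5.1 and Tables 14.3.6.4.1 and 14.3.6.4.2 as follows.

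1. Define baseline CO and CPO from Day of Implant (pre-implant) inputs. At every timepoint, take blood pressure from the same reading as SvO2 and SaO2, hemoglobin from the nearest draw, and the most recent weight: Day of Implant weight for baseline and 12 h, target-met weight at target met.
2. Add the paired change from Day of Implant to 12 h. Flag patients with any inotrope or diuretic change before that reading. Label it a before-after result free of planned drug adjustment, not an isolated pump effect.
3. Keep the target-met change and report it by whether any inotrope dose changed before the reading. First confirm where this value comes from: SAP 7.14 states, for urine output, that the target-met timepoint is not collected in the latest CRF, yet SAP 7.9.5.1 relies on it.

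The cost is SAP wording, programming of data already scheduled for collection, and a few extra table rows. The groups in item 3 will be small and should be read descriptively.
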